### 3.2 Primary Study Endpoints

#### Phase I:

The primary end points of Phase I are dose limiting toxicity and maximum tolerated dose. DLT, graded according to the Common Terminology Criteria of Adverse Events (CTCAE) version 4.0, will be defined as one or more of the following events occurring any time during the defined DLT period from initiation of HCQ (Week 0) to 1 month following second TACE (Week 12) excluding the day immediately following TACE: (1) grade 3 or higher hepatobiliary complication, except hepatic pain; (2) grade 4 or higher hepatic pain; (3) grade 3 or higher abnormality of liver function tests including total bilirubin (i.e. >3x the upper limit of normal) and transaminases (i.e. >5x the upper limit of normal, the Hospital of the University of Pennsylvania defines normal transaminases as AST < 41 IU/L and ALT < 63 IU/L); (4) grade 3 or higher elevation of serum creatinine (i.e >3x baseline or >3x upper limit of normal); (5) grade 3 or higher increase in international normalized ratio (i.e. greater than 2.5x upper limit of normal or >2.5x baseline if

CONFIDENTIAL

This material is the property of the University of Pennsylvania. Do not disclose or use except as authorized in writing by the study sponsor

anti-coagulated); or (6) any grade 3 or higher toxicity that is possibly or definitely related to treatment. Given the prevalence of baseline thrombocytopenia in patients with HCC, decreases in platelet count will not be evaluated as a DLT.

Prior investigations have demonstrated the safety of TACE for HCC with a reported rate of major complications related renal dysfunction, biliary injury, gastrointestinal tract ulcer, and treatment related mortality ranging between 2 and 3%(45). Rates of hepatic failure in multiple studies have averaged 7.5%(45).

Phase II:

The primary end point of Phase II will be rate of complete imaging response by mRECIST (see Imaging Assessment of Response under Section 3.3).

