### 3.4 Dose Reduction Schema

Toxicities will be evaluated using the Common Terminology Criteria of Adverse Events (CTCAE) version 4.0. Patients developing grade 3 or higher toxicity of any kind, which does not meet the definition of DLT, will call for holding HCQ therapy until the toxicity resolves to grade  $\leq 1$ . Any adverse effect attributed as possibly, probably or definitely related solely to HCQ will result in the dose being held until the adverse effect has resolved to  $\leq$  grade 1 or baseline. If the adverse effect resolves, reinstatement of treatment can occur but at a reduced dose as described below (HCQ Dose Reduction Schema). If the adverse effect recurs at the reduced dose, treatment will be held until the adverse effect has resolved to  $\leq$  grade 1 and when resolved treatment can be reinstated at the next lower dose level. No more than 2 dose reductions are allowed during the maintenance cycles.

Toxicities that may be attributable to HCQ include nausea, vomiting, diarrhea, rash, and visual field changes. If any of these adverse events occur at grade  $\leq 2$ , HCQ may be continued and the adverse event managed with supportive care. With particular regard to visual field deficits patients should be cautioned to report any visual symptoms, particularly difficulty seeing entire words or faces, intolerance to glare, decreased night vision, or loss of peripheral vision. These symptoms of peripheral retinal toxicity should prompt drug discontinuation and ophthalmologic evaluation.

Table: Hydroxychloroquine Dose Escalation Schema

Dose level	HCQ
-1a	200 mg qday (9AM)
1	400 mg qday (9AM)
2	400 mg BID (9AM/9PM)
3	600 mg BID (9AM/9PM)

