## **4.4 Early Withdrawal of Subjects**

### **4.4.1 When and How to Withdraw Subjects**

- PI Decision: Subjects may be withdrawn at any time during the study if the PI believes it is in the subject's best interest. In this event, the reasons for withdrawal will be documented.
- Subject Participation: Refusal to continue treatment, follow-up, comply with the protocol or withdrawal of consent. In this event, the reasons for withdrawal will be documented.

Patients withdrawing from the study will be entitled to pursue all treatment options available for the treatment of HCC without prejudice from the providing physicians.

Once the subject has discontinued treatment, the primary reason for discontinuing treatment must be clearly documented in the subject's records and on the CRF. The investigator will assess each subject for response at the time of withdrawal.

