### **4.4.2 Data Collection and Follow-up for Withdrawn Subjects**

Even though subjects may be withdrawn prematurely from the study, it is imperative to collect at least survival data on such subjects throughout the protocol defined follow-up period for that subject. Such data is important to the integrity of the final study analysis since early withdrawal could be related to the safety profile of the experimental therapy. If a subject withdraws consent to participate in the study, attempts will be made to obtain permission to record at least survival data up to the protocol-described end of subject follow-up period. Methods that may be used to obtain survival data will include phone calls to the subject, phone calls to next-of-kin if possible, and certified letters to the subject or next-of-kin. If permission to collect or the specific survival data cannot be obtained after 4 phone calls and 4 letters to the subject and/or next-of-kin, the patient will be regarded as lost to follow up.

CONFIDENTIAL

This material is the property of the University of Pennsylvania. Do not disclose or use except as authorized in writing by the study sponsor

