### 5.5 Subject Compliance Monitoring

Prior to TACE and with each follow-up phone call and clinical visit, the patient will be asked about their compliance with taking HCQ (e.g. patients will be asked if they have missed any doses of HCQ and this information will be recorded). Any reported missed doses will be recorded. Patients who miss greater than 5 consecutive days of therapy will be deemed non-compliant and asked to withdraw from the study. Non-compliant patients will be replaced in the dose escalation phase of the trial.

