## 7.3 Subject Population(s) for Analysis and Duration of Study

Analysis of both primary and secondary end points will be performed on an intention to treat basis. A maximum of 58 patients will be required if all 3 dose levels are investigated in the Phase I trial. If 1-2 patients are enrolled per month, then we expect up to approximately 5 years will be needed to complete enrollment.

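### Section 5.5 asks patients who stop HCQ for more than 5 days to leave the study, so the scan needed for the intention-to-treat complete response analysis is not assured

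*Combined protocol and SAP*

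**What the plan says.** Section 5.5 sets the rule: "Patients who miss greater than 5 consecutive days of therapy will be deemed non-compliant and asked to withdraw from the study". It adds that such patients are replaced during dose escalation and says nothing about replacement in Phase II.

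Section 4.4.1 makes the same link between drug and study. Its participation ground for withdrawal reads "Refusal to continue treatment, follow-up, comply with the protocol or withdrawal of consent". It then adds: "The investigator will assess each subject for response at the time of withdrawal". For patients who have left, section 4.4.2 says "it is imperative to collect at least survival data on such subjects throughout the protocol defined follow-up period".

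Section 3.2 defines the endpoint: "The primary end point of Phase II will be rate of complete imaging response by mRECIST". Section 7.3 defines the population: "Analysis of both primary and secondary end points will be performed on an intention to treat basis". Section 7.2 promises a CR rate with a 95% confidence interval and gives no rule for a patient without a response scan.

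The response scan falls at Week 12 for bilobar disease (6.9), at Week 14 for unilobar disease with a second TACE (6.10), and at Week 7 (3.1) or Week 8 (6.7) for other unilobar patients. HCQ starts about four weeks before the first TACE (3.1, 5.2).

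**The concern.** Under intention to treat, a patient who stops the tablets still counts in the CR rate, so the plan needs that patient's scan. Section 5.5 instead asks the patient to leave. No section describes a visit schedule for someone who is off HCQ but still in the study.

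The loss need not be random. Even if a missed dose means only one the patient chose not to take, the rule covers patients who stop because of side effects they find hard to bear. Stage 1 turns on 16 patients, so one or two missing scans can matter to the decision to continue.

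**Working it through.** **Does any provision secure the scan?**

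- The assessment at withdrawal (4.4.1) is tied to the day of leaving. Section 5.5 has compliance checked before TACE, so the rule can apply during the four-week lead-in, when there is no TACE response to measure. After TACE, a patient who leaves before the Week 7/8, 12 or 14 scan is assessed too early to replace it.
- Section 4.4.2 names survival data as the minimum. That serves overall survival, not CR.
- Sections 3.1 and 6.11 describe follow-up imaging as routine practice. Scans may therefore exist, but no text requires them to be collected for CR after withdrawal.

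**Inputs.** From section 7.1: 16 patients in stage 1, six of them from Phase I at the MTD; stop at 7 or fewer CR; 30 more patients; reject at 23 or more of 46; p0 = 0.40, p1 = 0.60. Assumed here: a share w of 5% or 10% leaves under 5.5.

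**The plan's own figures.**

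- Early stopping under the null is P(X ≤ 7), X ~ Bin(16, 0.40) = 0.716, matching the stated 72%.
- P(reject) = sum over x = 8 to 16 of P(X = x) × P(Y ≥ 23 − x), with X ~ Bin(16, p) and Y ~ Bin(30, p). This gives 0.077 at p = 0.40 and 0.829 at p = 0.60, against the stated 0.05 and 0.80.
- A cut-off of 24 gives 0.049 and 0.801. That mismatch is a separate matter. The printed rule is used below, with 24 as a sensitivity check.

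**Effect on power.** If scans are lost and counted as non-CR, p = 0.60 × (1 − w). If scans are kept and patients off HCQ respond at the protocol's TACE-alone rate, p = 0.60 × (1 − w) + 0.40 × w. In the replacement case, the six Phase I places in stage 1 keep p = 0.60 and the other 40 patients take the reduced p.

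| Case | w = 5% | w = 10% |
|---|---|---|
| p, scans lost | 0.57 | 0.54 |
| Power, scans lost | 0.736 | 0.617 |
| Power, scans lost, six places replaced | 0.76 | 0.68 |
| p, scans kept, 40% off HCQ | 0.59 | 0.58 |
| Power, scans kept | 0.801 | 0.770 |
| Power, scans kept, six places replaced | 0.81 | 0.79 |

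Without replacements, keeping the scans recovers (0.801 − 0.736)/(0.829 − 0.736) = 0.70 of the loss at 5%, and (0.770 − 0.617)/(0.829 − 0.617) = 0.72 at 10%. If patients off HCQ respond at 60%, all of it is recovered. With the cut-off at 24, power falls from 0.801 to 0.690 or 0.554 with scans lost, and is 0.767 or 0.730 with scans kept.

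**Stage 1.** The chance of the 8 CRs needed to continue is 0.858 at a CR rate of 60%. With m scans lost it is P(Bin(16 − m, 0.60) ≥ 8): 0.787 for m = 1 and 0.692 for m = 2. With those scans kept and a 40% response it is 0.834 and 0.808. Three lost scans would give 0.574. Three or more losses among 16 has probability of only 4% at w = 5% and 21% at w = 10%, and among the 10 patients outside Phase I, 1% and 7%.

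**The case against.** Several stronger readings are tempting, and the documents do not support them.

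- **That no image is taken at withdrawal, or that scans are necessarily lost.** The only response definitions in the protocol are the mRECIST and EASL imaging criteria, so the assessment in 4.4.1 most naturally means imaging. Survival data is a floor, routine post-TACE scans may exist, and some unilobar patients will already have their Week 7/8 scan. The rule is also only a request to leave. What stands is that the scheduled scan is not assured.
- **That a dose hold of more than 5 days triggers withdrawal.** Under section 3.4, grade 3 or higher toxicity outside the DLT definition "will call for holding HCQ therapy until the toxicity resolves to grade" 1 or lower, and for effects attributed to HCQ alone, "If the adverse effect resolves, reinstatement of treatment can occur but at a reduced dose". Treating a directed hold as non-compliance would defeat that provision. Section 5.5 does not state the exemption, so a clarification is useful, but no contradiction is shown.
- **That the MTD is biased or laboratory DLTs are missed.** Section 3.1 keeps everyone with at least one day of HCQ in the toxicity analysis, and section 8.2 requires adverse events to be recorded until 6 months after the last dose. No such bias is shown.
- **That power will be 0.62.** The withdrawal rates are assumed, every such patient is taken to have no usable scan, and the plan has no rule that counts a missing scan as non-CR. If the 60% target already allows for imperfect adherence, reducing it again counts some of the loss twice.

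The affected group is also narrow. Treatment-related grade 3 or higher toxicity is already a DLT, and section 3.4 lets the listed HCQ effects at grade 2 or lower be managed on drug, apart from visual symptoms. These points limit the size of the problem. They do not supply the missing scan.

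**Conclusion.** The concern holds within limits. Followed as written, sections 5.5 and 4.4.1 can remove a patient from scheduled imaging while section 7.3 keeps that patient in an imaging-based primary analysis. The gap matters for patients who leave before TACE or before their response scan is due.

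At an assumed 5% or 10% withdrawal, the power figures with scans lost (0.74 or 0.62; 0.76 or 0.68 with Phase I replacements) are upper bounds on the harm, not forecasts. Keeping the scans brings power close to the base of 0.83 without fully restoring it, unless patients off HCQ respond as well as those on it. How often this will happen cannot be judged from the documents. The change is worth making because it is cheap and brings the conduct rule into line with the analysis the plan already chose.

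**What to change.** In 5.5, replace the request to leave the study with discontinuation of HCQ only. Planned TACE goes ahead if clinically appropriate; scheduled imaging, laboratory tests and AE/DLT follow-up continue; and the patient stays in the intention-to-treat CR analysis. In 4.4.1, state that refusing further HCQ does not by itself amount to study withdrawal. Optionally, add to 5.5 that doses held or stopped under 3.4 are not missed doses. Phase I replacement can stay as written, with DLTs already observed still counted.

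The cost is a few sentences. The TACE sessions, scans and laboratory tests are already planned, and the sample size and decision boundaries do not change. The downside is that some patients with reduced HCQ exposure contribute to the CR rate. If they respond at 40%, the expected rate is 0.95 × 60% + 0.05 × 40% = 59%, or 0.90 × 60% + 0.10 × 40% = 58%. Section 7.3 already accepts that dilution. The change does not settle how scans missing for other reasons are counted; section 7.2 would need its own rule for those.

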### 5.6 Prior and Concomitant Therapy

CONFIDENTIAL

This material is the property of the University of Pennsylvania. Do not disclose or use except as authorized in writing by the study sponsor

No other concomitant locoregional therapies for HCC will be accepted. Patients who have received prior locoregional treatments for HCC may be enrolled if these tumors are no longer viable and patient is now being referred to IR for TACE to treat newly identified HCCs.

HCQ has known effects on P450 enzymes, patients requiring anti-convulsants may be treated with any of the non-enzyme inducing anti-convulsants which include: felbamate, valproic acid, gabapentin, lamotrigine, tiagabine, topiramate, zonisamide, or levetiracetam. For nausea, aprepitant should be avoided.

### **5.7 Blinding of Study Drug**

This protocol does not utilize blinding. Subjects and investigators will know the treatment being administered.

### **5.8 Receiving, Storage, Dispensing and Return**

#### **5.8.1 Receipt of Drug Supplies**

Since hydroxychloroquine is an FDA approved drug, the prescription may be filled at a pharmacy, which is most convenient to the patient. Thus, no special procedures for receipt of the study drug are needed.

#### **5.8.2 Storage**

Since hydroxychloroquine is an FDA approved drug, no special procedures for storage of the study drug are needed.

#### **5.8.3 Dispensing of Study Drug**

Since hydroxychloroquine is an FDA approved drug, no special procedures for distribution of the study drug are needed.

#### **5.8.4 Return or Destruction of Study Drug**

Since hydroxychloroquine is an FDA approved drug, no special procedures for return of the study drug are needed. Unused HCQ may be disposed by the patient as they would with non-study prescription medication (e.g. based on the regulations of the municipality in which they live)..

## **6 Study Procedures**

*Please Note - All visits will be by calendar week. All visits from Weeks 0 to 14 will have a grace period of 14 days/2 weeks to allow for scheduling of procedures, weekends, holidays as well as off service days for the interventionalist while not exceeding a total of 15 weeks total time taking HCQ. In addition, all study visits/events are sequential so that a patient cannot proceed to a study visit without completing the prior visit (e.g. Week 2 visit events must be completed before the Week 3 visit, Weeks 3 visit events must be completed before Week 4 visit, etc.).*

### **6.1 Week 0:**

All patients will undergo a standard of care consult office visit with IR at which time they will be approached about study consent and screened for eligibility. As soon as possible after patients' complete the study informed consent process, patients will begin HCQ therapy.

### **6.2 Week 2:**

All patients will have laboratory assessments (Complete Blood Count, PT/INR, Complete Metabolic Panel) to check for DLT.

CONFIDENTIAL

This material is the property of the University of Pennsylvania. Do not disclose or use except as authorized in writing by the study sponsor

### **6.3 Week 3:**

All patients will be contacted by phone after receiving the laboratory results to verify compliance with HCQ therapy and discuss toxicity and AEs.

### **6.4 Week 4:**

All patients will undergo initial TACE. A single session of TACE can be used to treat all lesions within one lobe of the liver.

### **6.5 Week 6:**

All patients will have laboratory assessments (CBC, PT/INR, CMP) to check for DLT.

### **6.6 Week 7:**

All patients will be contacted by phone after receiving the laboratory results to verify compliance with HCQ therapy and discuss toxicity and AEs.

### **6.7 Week 8:**

Patients with **bilobar disease** will undergo TACE of the contra-lateral lobe to treat additional HCC. This second session of TACE will be performed only if the patient's clinical status and laboratory assessments have returned to baseline and the patient has not had any dose limiting toxicity.

Patients with **unilobar disease** will undergo an IR clinical office visit. At the clinical office visit - compliance with HCQ therapy, toxicity and AEs will be recorded. In order to determine if a second session of TACE is needed for subjects, a response assessment with imaging (contrast enhanced MRI or CT) will also be conducted at this visit.

### **6.8 Week 10:**

Patients with **bilobar disease** and patients with **unilobar disease not undergoing a second session of TACE** will have laboratory assessments (CBC, PT/INR, CMP) to check for DLT.

Other patients with **unilobar disease** will undergo second session of TACE. This second session of TACE will be performed only if 1.) the HCC is less than PR by mRECIST or new HCC has developed since the initial TACE, 2.) the patient's clinical status and laboratory assessments have returned to baseline and 3.) the patient has not had any dose limiting toxicity.

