Following TACE of the contra-lateral lobe, the patient will undergo repeat CBC, CMP and PT/INR at Week 10 to evaluate for dose limiting hepatotoxicity and nephrotoxicity. At Week 12, the patient will be evaluated with a clinical office visit, and contrast enhanced MRI or CT to assess imaging response of combined therapy. Patients will then undergo follow-up with clinical office visit, laboratory studies and imaging at 3 months (+/- 1 week) and 6 months (+/- 1 week) as part of routine clinical practice following TACE(41). Post-treatment imaging of all enrolled patients will be reviewed by a radiologist from the Abramson Cancer Center Clinical Imaging Core blinded to dose of HCQ. Post-treatment imaging will be assessed for mRECIST and EASL response to therapy and percentage of residual viable tumor. Response to therapy and progression of disease will be categorized using previously published mRECIST and EASL criteria (see Imaging Assessment of Response under Section 3.3)(42,43). These imaging criteria take into account percent necrosis as estimated by absence of tumor enhancement in addition to size reduction, and have been shown to correlate well with histopathologic data(13,44).

Follow-up study period to examine for late toxicity will end 6 months after cessation of HCQ therapy.

CONFIDENTIAL

This material is the property of the University of Pennsylvania. Do not disclose or use except as authorized in writing by the study sponsor

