**Timeline Unilobar HCC**

For patients with unilobar HCC, duration of HCQ therapy, frequency/timing of laboratory assessments, and definition of DLTs will be the same as with bilobar HCC. However, imaging, response assessment to initial TACE and phone call or clinical office visit following initial TACE will be performed at calendar Week 7. Repeat chemo-embolization may be performed at calendar Week 8 on HCCs with less than PR by mRECIST (see Imaging Assessment of Response under Section 3.3) or new HCCs which have developed since the initial TACE so long as LFTs are below the threshold of dose limiting toxicity. Subsequent follow-up clinic visits and imaging will be the same as with bilobar HCC - 3 months (+/- 1 week) and 6 months (+/- 1 week) following the last clinic visit.

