### **6.9 Week 12:**

Patients with **bilobar disease** will undergo a contrast enhanced MR or CT, IR clinical office visit and response assessment. At the clinical office visit - compliance with HCQ therapy, toxicity and AEs will be recorded.

Patients with **unilobar disease** that **did not** undergo a **second session of TACE** will have an IR clinical phone call where compliance with HCQ therapy, toxicity and AEs will be recorded.

Patients with **unilobar disease** that **did** undergo a **second session of TACE** will not have any required study procedures at this time point.

CONFIDENTIAL

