### **6.10 Week 14:**

Patients with **unilobar disease** that **did undergo** a **second session of TACE** will undergo a contrast enhanced MR or CT, IR clinical office visit and response assessment. At the clinical office visit - compliance with HCQ therapy, toxicity and AEs will be recorded.

Patients with **bilobar disease** and patients with **unilobar disease that did not undergo a second session of TACE** will not have any required study procedures at this time point.

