### **6.11 Follow-Up Q3 Months:**

Study follow-up of patients will occur at 3 months (+/- 1 week) and 6 months (+/- 1 week) after cessation of HCQ therapy (Week 12 or Week 14). The 3 month and 6 month follow-up visits will include contrast enhanced MRI or CT, laboratory assessments (CBC, PT/INR, CMP) and IR clinical office visits by an interventional radiologist. The follow-up study period will end at 6 months (+/- 1 week) after cessation of HCQ therapy (Week 12) to examine for late toxicity. Patients will continue to be followed beyond the end of follow-up study period per normal Interventional Radiology standard of care and *only* patient data regarding tumor progression and survival will be recorded during this time period to better assess LPFS and overall survival.

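### Sections 3.1 and 6 disagree on second TACE and labs in unilobar disease, and under Section 6 re-embolised patients have no scheduled blood sample between that TACE and the end of the DLT window

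*Combined protocol and SAP*

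**What the plan says.** **Section 3.1, Timeline Bilobar HCC.** The second TACE is at Week 8. Afterwards "the patient will undergo repeat CBC, CMP and PT/INR at Week 10 to evaluate for dose limiting hepatotoxicity and nephrotoxicity".

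**Section 3.1, Timeline Unilobar HCC.** For these patients "frequency/timing of laboratory assessments, and definition of DLTs will be the same as with bilobar HCC". Response imaging is at Week 7, and repeat TACE may follow at Week 8.

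**Section 6, unilobar patient who is re-embolised:**

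- Week 6 (6.5): "All patients will have laboratory assessments (CBC, PT/INR, CMP) to check for DLT".
- Week 8 (6.7): office visit with response imaging. "At the clinical office visit - compliance with HCQ therapy, toxicity and AEs will be recorded". No labs are listed.
- Week 10 (6.8): second TACE, provided that, among other conditions, "the patient's clinical status and laboratory assessments have returned to baseline". The Week 10 panel is assigned to bilobar patients and to unilobar patients not having a second TACE.
- Week 12 (6.9): they "will not have any required study procedures at this time point".
- Week 14 (6.10): they "will undergo a contrast enhanced MR or CT, IR clinical office visit and response assessment". Compliance, toxicity and AEs are recorded; no labs are listed.
- Follow-up (6.11): labs at 3 and 6 months after HCQ stops.

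**DLT window.** Sections 3.1 and 3.2 end it at Week 12, or Day 56 to 63, and describe that as 4 weeks or 1 month after the second TACE. The criteria include grade 3 or higher liver function tests, creatinine and INR.

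**The concern.** Three of the DLT criteria can be read only from a blood sample. The protocol treats the period after a second TACE as one that needs such a sample: bilobar patients have a panel two weeks after it, expressly to look for hepatic and renal DLTs, and Section 3.1 promises unilobar patients the same timing. Section 8.3.4 also makes hepatic and renal toxicity after the initial TACE an event of special interest. Section 6 does not deliver the promised panel to the unilobar patients who receive more embolisation, and it gives no reason.

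These patients can count toward escalation and the MTD. In the 3+3 table of Section 3.1, one unrecorded DLT changes the decision:

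- 1 of 3 (enrol three more) becomes 0 of 3 (escalate).
- 2 of 6 (dose exceeds the MTD) becomes 1 of 6 (escalate, or MTD at the top level).

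A site could follow Section 6 to the letter and record no DLT for a patient who has no laboratory value after the second TACE.

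**Working it through.** **1. Calendar.** The first TACE is at Week 4, so Day = (Week − 4) × 7. Week 6 = Day 14, Week 8 = Day 28, Week 10 = Day 42, Week 12 = Day 56, Week 13 = Day 63, Week 14 = Day 70.

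**2. The plan's own window.** A second TACE at Week 8 plus 4 weeks is 28 + 28 = Day 56 = Week 12. This reproduces the start of the stated Day 56 to 63 range. The window was therefore built on a Week 8 second TACE, as in bilobar patients and in Section 3.1's unilobar text.

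**3. The same window with Section 6's unilobar TACE.** At Week 10 (Day 42), Day 56 to 63 is only 14 to 21 days after the procedure. Four weeks after it is 42 + 28 = Day 70 = Week 14.

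**4. Scheduled on-treatment panels under Section 6.**

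| Group | Panels (week) | Second TACE | Panels after second TACE, inside DLT window |
|---|---|---|---|
| Bilobar | 2, 6, 10 | Week 8 | 1 |
| Unilobar, not re-embolised | 2, 6, 10 | none | not applicable |
| Unilobar, re-embolised | 2, 6 | Week 10 | 0 |

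The zero holds whether the window ends at Week 12, Day 63 or Week 14.

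**5. Next listed panel.** Three months is about 13 weeks. HCQ stops at Week 12 or 14, so the visit falls at 12 + 13 = Week 25 or 14 + 13 = Week 27.

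- After the second TACE: 25 − 10 = 15 to 27 − 10 = 17 weeks.
- After the window closes: 25 − 14 = 11 to 27 − 12 = 15 weeks.

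That is too late to register a DLT on any reading.

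**6. Section 3.1 followed on its own.** With TACE at Week 8 and labs at Week 10, one panel falls 2 weeks after TACE and inside the window. The gap does not exist.

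**7. The two mixed.** With Section 3.1's Week 10 panel and Section 6's Week 10 TACE, sample and procedure share a nominal week. One draw cannot serve both as a pre-procedure check and as a sample two weeks afterwards.

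**8. Age of the last scheduled panel at the second TACE (nominal).** Unilobar under Section 6: 42 − 14 = 28 days. Bilobar: 28 − 14 = 14 days.

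**The case against.** The strongest reply is that the protocol does schedule these labs, because Section 3.1's unilobar text gives the bilobar lab timing. That stands for Section 3.1 followed alone. It does not settle the matter, since Section 6 places the TACE two weeks later and expressly limits who has the Week 10 panel.

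Other safeguards exist:

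- The unilobar timeline figure is not shown, and the site's TACE standard is only cited. Either may include labs. Pre-procedure labs alone would not supply a value after TACE.
- Under Section 8.1, an abnormal result can prompt more frequent checks. That leaves a new, silent change after a normal Week 6 panel.
- Section 8.6 bars escalation until the medical monitor has reviewed records for DLT. The review might notice a missing panel but cannot replace it.
- Symptomatic events can still be reported, including at the Week 14 visit.
- Silent laboratory DLTs are probably uncommon. Section 1.1 says that most studies show liver tests normalising by one week after TACE, and Section 1.5 reports no hepatic toxicity in the HCQ cancer trials.

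A reader might go further and infer that re-embolising on a nominally 28-day-old panel is itself an error. The documents do not support that. Section 6.8 does not tie its return-to-baseline condition to the Week 6 sample and sets no maximum sample age. The only age limit given is 30 days, for baseline labs before enrolment (Section 3.1), which is a different step.

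**Conclusion.** The concern holds as a conflict between Sections 3.1 and 6 that, under Section 6, leaves a gap in DLT ascertainment. For re-embolised unilobar patients Section 6 schedules no sample between the second TACE and the end of the DLT window, against one for bilobar patients. The laboratory DLT criteria are therefore not measured on schedule after that TACE. This rests on the text of Section 6 as it stands and on nominal visit weeks; it would change if the missing figure lists a panel after TACE.

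The severity is minor. A reader might infer that the MTD is likely to be wrong, but the documents give no unilobar share, no re-embolisation rate and no rate of silent laboratory DLTs, so no such probability can be calculated. Nothing here bears on the complete response rate or the power of Phase II.

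**What to change.** 1. State whether Section 3.1 or Section 6 governs the timing of second TACE and labs in unilobar disease, and align the other section with it. If Section 3.1 governs, its Week 8 TACE and Week 10 panel already close the gap.
2. If Section 6 governs, draw the existing CBC, CMP and PT/INR panel at Week 12 in re-embolised unilobar patients. That is two weeks after the second TACE, as in bilobar patients, and falls by the end of the window on every reading. Alternatively, draw it at the Week 14 visit they already attend, and restate in Sections 3.1 and 3.2 that their DLT window ends at Week 14.
3. Do not count such a patient as observed for escalation until that panel is back.
4. Optionally, add the same panel at the existing unilobar Week 8 visit for patients going on to a second TACE. The return-to-baseline condition could then use a nominally 2-week-old sample, as in bilobar patients.

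The cost is one routine panel per re-embolised unilobar patient, or two with the optional draw, plus wording changes. The Week 12 draw may need a lab-only attendance; the Week 14 draw does not. Escalation may wait briefly on a result, and a DLT that would have been missed could enlarge a cohort. No extra panels are needed for other patients.
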